14.5.3 Primary Analysis

The co-primary efficacy endpoints, assessed in the male subjects, are:

1. The change from baseline of the average of the Week 4, Week 8 and Week 12 IIEF-EF domain scores
2. The change in percentage of sexual intercourse attempts in which subjects were able to insert their penis into their partner's vagina (SEP Question 2) between baseline and the 12 week treatment period
3. The change in percentage of sexual intercourse attempts in which subjects were able to maintain an erection of sufficient duration to have successful intercourse (SEP Question 3) between baseline and the 12 week treatment period

Baseline for the IIEF-EF score is the assessment at Visit 2, baseline for SEP Questions 2 and 3 is the percentage in the screening, treatment free, 4-week period.

The primary objective will be assessed by testing the following hypotheses for each MED2005 dose group (0.6 mg GTN, 1.2 mg GTN or 1.8 mg GTN) and each co-primary endpoint separately, using the FAS:

Null hypothesis (H0): There is no difference in the mean change from baseline in the IIEF-EF domain, SEP Question 2 and SEP Question 3 for the MED2005 treatment group compared with placebo.

$$H0: \mu (\text{MED2005}) = \mu (\text{placebo})$$

Alternative hypothesis (H1): There is a difference in the mean change from baseline in the IIEF-EF domain, SEP Question 2 and SEP Question 3 for the MED2005 treatment group compared with placebo.

$$H1: \mu (\text{active}) \neq \mu (\text{placebo})$$

Each comparison will be carried out at the two-sided 5% level of statistical significance after a Bonferroni correction (p-values multiplied by three). Efficacy will be stated if all null hypotheses for the co-primary endpoints are rejected. However, the three co-primary endpoints will still be considered in a hierarchy of their importance, with the testing order being IIEF-EF domain, SEP Question 3 and SEP Question 2.

The statistical model for the primary analysis of the IIEF-EF will be an analysis of covariance (ANCOVA) including terms for treatment group, site and baseline (as a continuous variable). The statistical model for the primary analyses of SEP Question 2 and SEP Question 3 will be an ANCOVA including terms for treatment group, site, baseline (as a continuous variable) and baseline ED severity (categorical variable). As the endpoints are change from baseline assessment, the respective baselines for each endpoint are included in the analyses. Baseline ED severity, used as part of the randomisation scheme, is a categorical grouping of the baseline IIEF-EF and as such is not included in the primary analysis of the IIEF-EF as it already appears in the model as a continuous variable. A sensitivity analysis will be performed including baseline ED severity (categorical variable) in addition to the variables included in the primary analysis. The estimated treatment means and differences (MED2005 versus placebo) will be reported as part of this analysis.

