8.2.3 Rationale for Study Drug Dose and Schedule

The justification for choice of doses to be tested in this study was based on PK and clinical data generated in earlier developmental studies with MED2005, and the clinical use of a 2.5 mg gel of GTN in a related FMD product.

FMD has previously tested the following doses of MED2005:

FMD study	Dose	Phase	Number of Volunteers/Patients
FM33	MED2003 0.075 mg, 0.1 mg, 0.25 mg, 0.5 mg MED2004 0.75 mg MED2005 1.2 mg	I	16 healthy volunteers
FM35	MED2003 0.01 mg, 0.075 mg, 0.25 mg MED2005 0.6 mg	I	15 healthy volunteers
FM53	MED2005 0.6 mg	IIa	232 patients
FM58	MED2005 0.6 mg, 1.2 mg, 1.8 mg, 2.4 mg	I	30 healthy volunteers

In the FM58 PK study, MED2005 0.6 mg, 1.2 mg, and 1.8 mg demonstrated similar or lower PK values than the sublingual tablet comparator (Nitrostat 1.8mg GTN); however, in some of the PK parameters the MED2005 2.4 mg was slightly higher compared to Nitrostat. There were no safety concerns for any of the studied doses of MED2005.

FMD currently market a condom based product with an ancillary medicinal substance. The class III medical device incorporates a topical gel which contains 2.5 mg GTN in a non-aqueous base and is used to help maintain an erection. Users are exposed to the topical application of 2.5 mg of GTN under the occlusion of the device. The extended clinical use of a 2.5 mg GTN gel in a class III has a validated satisfactory safety record.

Therefore MED2005 0.6 mg, 1.2 mg, and 1.8 mg were selected for the double-blind phase of this study. For the open-label extension phase, all subjects will be provided with MED2005 1.8 mg as this dose is expected to have the greatest efficacy and provide the most significant information on safety and efficacy.

During the double-blind phase subjects are asked to make at least four intercourse attempts using the IMP in each of the three 4-weekly period during treatment in order to get a reasonable assessment of the efficacy and safety of MED2005 versus placebo.

The open-label extension phase is designed to assess long-term safety of MED2005 as it might be used once it is on the market. Therefore, subjects will be asked to use the IMP as and when they wish to and medication use will be assessed as part of the open-label analyses.

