14. STATISTICAL ANALYSES

Further details of the proposed statistical analysis will be documented in the statistical analysis plan (SAP), which will be written following completion of the protocol and finalised prior to the breaking of the blind.

In general, safety and efficacy variables will be presented by means of descriptive statistics and figures, as appropriate, by treatment (active at each dose level and placebo) and by time point and gender, if applicable. Continuous variables will be summarised using the number of non-missing observations, mean, standard deviation (SD), median, first and third quartiles, minimum and maximum. Categorical variables will be presented using number of subjects and percentages. For ordered categorical variables, cumulative percentages may also be presented. Raw data will be listed.

Baseline values will be the last assessments prior to randomisation at Visit 2 unless stated otherwise.

A Bonferroni correction will be used to take into account that there are three active versus placebo comparisons; i.e. all p-values resulting from comparing the three different MED2005 doses (0.6 mg GTN, 1.2 mg GTN, 1.8 mg GTN) versus placebo will be multiplied by three and statistical significance will then be declared if $p < 0.05$. Corresponding Bonferroni corrected 95% confidence intervals will be produced.

The objective for the double-blind phase is for all co-primary endpoints to show superiority of MED2005 to placebo in order to conclude a significant result of the study. For this objective, no adjustment for multiplicity of the error probability for the individual co-primary endpoints is required. However, the three co-primary endpoints will still be considered in a hierarchy of their importance, with the testing order being IIEF-EF domain, SEP Question 3 and SEP Question 2.

The objective of the open-label extension phase is to evaluate the safety of long-term (up to 12 months) use of MED2005. In addition, the long-term efficacy of MED2005 will be evaluated. Both safety and efficacy will be evaluated in the subset of subjects who completed the double-blind phase and took part in the open-label extension phase. Descriptive statistics will be based on observed data. In case of any randomisation/treatment errors, any summaries split by treatment group will be produced according to treatment received.

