14.7 Sample Size

A sample size of $n = 250$ per group (total $N = 1000$) provides 90% study power to reject the null hypotheses for all three primary endpoints when comparing a MED2005 dose to placebo, using a Bonferroni corrected type I error, adjusting for three dose versus placebo comparisons. The sample size calculations were performed using EAST 6.4 in the continuous endpoint two-sample multiple comparisons multiple endpoints platform using the assumptions described below.

It is assumed that MED2005 is slightly better than alprostadil [33]. For the higher two doses alprostadil saw an improvement compared to placebo for IIEF-EF of 3.2 and 3.1 (least squares [LS] mean changes), giving an average of 3.15, for SEP Question 2 of 9.6 and 11.3 (LS mean changes), giving an average of 10.65, and for SEP Question 3 of 13.4 and 8.7 (LS mean changes), giving an average of 11.05. In Study FM53 there was a better improvement in SEP Question 3 than SEP Question 2 so the sample size assumptions take this into account. PDE 5's also appear to find SEP Question 2 more difficult to improve compared to placebo than SEP Question 3. Compared with the alprostadil results therefore it is assumed that the difference of MED2005 minus placebo for IIEF-EF is 3.2, for SEP Question 2 is 11.5 and for SEP Question 3 is 12.

Estimates of standard deviations are based on FM53 and published results from other ED treatments and are assumed to be 5.6, 33 and 33 for IIEF-EF, SEP Question 2 and Question 3, respectively [33, 34]. The differences between MED2005 and placebo for each endpoint are assumed to follow a multivariate normal distribution with the following correlation matrix, based on observed data from study FM53.

	IIEF-EF	SEP Question 2	SEP Question 3
IIEF-EF	1	0.5	0.5
SEP Question 2	0.5	1	0.6
SEP Question 3	0.5	0.6	1

For the open-label extension phase it is planned to recruit a total of 450 male subjects in order to meet ICH requirements.

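### Optional improvement: Holm's step-down rule for the dose-level efficacy claim keeps the two-sided 5% bound, loses no Bonferroni dose claim and can add some

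*Protocol*

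**What the plan says.** Section 14 of the protocol sets the rule across doses: "A Bonferroni correction will be used to take into account that there are three active versus placebo comparisons". It adds that "Corresponding Bonferroni corrected 95% confidence intervals will be produced". The Synopsis says the same, and section 14.5.3 applies it to the primary analysis: "Each comparison will be carried out at the two-sided 5% level of statistical significance after a Bonferroni correction (p-values multiplied by three".

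Within a dose, all three co-primary endpoints must succeed. Section 14.5.3 says "Efficacy will be stated if all null hypotheses for the co-primary endpoints are rejected", and section 14 asks "for all co-primary endpoints to show superiority of MED2005 to placebo in order to conclude a significant result of the study". The significance level is not split across endpoints. The stated hierarchy, "with the testing order being IIEF-EF domain, SEP Question 3 and SEP Question 2", ranks endpoints and not doses. No step-down over doses is given.

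Section 14.7 sizes the trial on the same footing, "using a Bonferroni corrected type I error, adjusting for three dose versus placebo comparisons", with one common effect for any dose. Section 8.2.3 says of 1.8 mg that "this dose is expected to have the greatest efficacy".

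**The concern.** Nothing here is invalid. The question is whether the rule gives away power that the 5% bound does not require.

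Single-step Bonferroni holds each dose to 0.05/3 whatever happens to the others. Once one dose has been declared effective, only two dose hypotheses remain that could be falsely rejected, so the remaining doses can be tested at a less strict level without exceeding 5%. Holm's procedure does this.

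The trial is dose-ranging and makes a separate efficacy statement for each dose. The sample size assumes the same effect in all three, while section 8.2.3 expects the top dose to do best. If the lower doses do less than planned, their power is below 90%, and they are the doses a step-down rule mainly helps.

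**Working it through.** **Inputs.** From section 14.7: 250 per group; effects 3.2 (IIEF-EF), 11.5 (SEP Q2) and 12 (SEP Q3); SDs 5.6, 33 and 33; correlations 0.5, 0.5 and 0.6. From sections 14 and 14.5.3: two-sided 5%, three doses, all three endpoints required. Allocation is 1:1:1:1 (section 9.5), so the dose-versus-placebo statistics share the placebo arm and correlate 0.5.

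**Reproducing the stated power.** The Bonferroni level is 0.05/3 = 0.01667, with two-sided critical value 2.394. The standard error is SD × √(2/250). Power is approximately Φ(effect/SE − 2.394).

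- IIEF-EF: SE 0.501, 3.2/0.501 = 6.39, power 0.99997
- SEP Q2: SE 2.952, 11.5/2.952 = 3.90, power 0.9335
- SEP Q3: SE 2.952, 12/2.952 = 4.07, power 0.9527

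With the stated correlations, the joint probability of winning on all three is 90.4%. The smallest group size giving 90% is 248. The protocol's 90% is therefore correct.

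**Why Holm is valid here.** A dose-level null is true if at least one of that dose's endpoint nulls is true. The largest of its three p-values cannot be smaller than the p-value of that true null, so it is a valid p-value for the dose. Holm orders the three dose p-values and tests them at 0.05/3, 0.05/2 and 0.05, stopping at the first failure. This controls the family-wise error at 5% under any dependence. No step is stricter than 0.05/3, so every dose that Bonferroni claims is still claimed.

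**Power per dose.** Each scenario used 400,000 simulated trials with two-sided z-tests. A claim was counted only if all three estimates favoured MED2005. Doses are listed as 0.6/1.2/1.8 mg. The graded patterns are assumptions, because the protocol gives no dose-response.

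| True effect (share of plan) | Bonferroni | Holm | Trials with an added claim |
|---|---|---|---|
| 100% in all doses | 90.4% each | 94.7% each | 12.1% |
| 75/87.5/100% | 60/78/90.5% | 73/85/92.8% | 20.6% |
| 50/75/100% | 20/60/90.4% | 33/67/91.3% | 19.6% |
| 25/50/100% | 2.0/20.1/90.4% | 4.7/25.2/90.5% | 7.5% |
| Two doses active | 90.4% each | 92.3% each | about 4% |
| One dose active | 90.4% | 90.4% | about 0.1% |

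At planning effects the mean number of doses claimed rises from 2.71 to 2.84, and the chance of claiming all three from about 79% to about 90%. The chance of claiming at least one is about 98.6% under both rules. No Bonferroni claim was lost in any scenario.

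**Error in the worst partial nulls** (SEP Q2 null at the stated doses, everything else certain to succeed):

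| Null doses | Two-sided, Bonferroni to Holm | Stated as efficacy (right direction), Bonferroni to Holm |
|---|---|---|
| One | 1.67% to 5.03% (theory 5.0%, Monte Carlo SE 0.03%) | 0.82% to 2.51% |
| Two | 3.15% to 4.65% | 1.55% to 2.31% |
| Three | 4.46% under both | 2.24% under both |

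**A version that fails.** Running Holm separately within each endpoint and then requiring all three is not safe. When each dose is null on a different endpoint, its family-wise error reached 13.7%. The rule with one p-value per dose gave 4.8% in the same setting.

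**The case against.** The case for leaving the text alone is a fair one. The rule is valid, consistent across four sections and delivers the stated power. Section 14.7 powers one dose against placebo, and that target is already met. The chance of at least one success does not move, 1.8 mg gains only about 0 to 2 points in the graded cases, and doses well below plan stay underpowered under either rule.

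Holm also has costs:

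- Every added claim has at least one co-primary whose Bonferroni-corrected interval includes zero and whose tripled p-value is 0.05 or more. The report would state efficacy for that dose beside a co-primary shown as non-significant.
- In the worst case, the error for a single ineffective dose triples.
- Because section 14.5.3 tests each endpoint separately, someone could apply Holm within endpoints, which breaks the error control.
- Other procedures exist, such as a fixed sequence starting from the highest dose.

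The costs in intervals and partial-null error are real and belong in the text, and they mean this is no more than an optional change. The within-endpoint hazard is removed by requiring a single p-value per dose. The endpoint order cannot affect a claim that needs all three endpoints. A fixed sequence can lose a dose claim that Bonferroni would make, and Holm cannot.

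**Conclusion.** The point holds as an inexpensive improvement and does not identify an error. For the dose-level efficacy statement alone, Holm on each dose's largest co-primary p-value makes every claim Bonferroni makes, and sometimes more, at the same family-wise bound. The gain is 4.3 points per dose (90.4% to 94.7%) at planning effects. In the graded cases it is about 3 to 13 points for the two lower doses, and it is nil if only one dose works.

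These figures rest on the effects, SDs and correlations of section 14.7, full groups of 250, normal approximation and, for the graded rows, assumed dose patterns. Error control and the absence of lost claims depend on none of the assumed effects, SDs, correlations or dose patterns. A sponsor who wants tests that always agree with the intervals, or the lower partial-null error, can reasonably keep Bonferroni.

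**What to change.** Before unblinding, reword section 14.5.3 and bring section 14 and the Synopsis into line:

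1. For each dose, take the largest unadjusted two-sided p-value over IIEF-EF, SEP Q3 and SEP Q2. Order the three values and test them at 0.05/3, 0.05/2 and 0.05, stopping at the first failure. State efficacy for a dose only if it is rejected and all three estimates favour MED2005, in keeping with the superiority wording of section 14.
2. Keep the tripled p-values and Bonferroni-corrected 95% intervals for the nine endpoint-by-dose comparisons and for all other endpoints. As now, no single endpoint result supports an efficacy claim. This layer is still needed: at planning effects, IIEF-EF falls below 0.05/3 in a dose that Holm does not claim in 5.3% of doses.
3. Keep the endpoint order for reporting within a dose.
4. State that Holm governs only the dose-level claim, is applied to one p-value per dose and is never run within an endpoint. State also that a claimed dose may have a corrected interval that includes zero.

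Section 14.7 can stand, with 90% read as a lower bound under its assumptions. The change is wording only and needs no extra patients or data. The costs to accept are the interval mismatch (12.1% of trials at planning effects, 7.5% to 20.6% in the graded cases) and the higher partial-null error, which stays within the nominal level.

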14.5.4 Other Efficacy Variables

All other efficacy variables will be analysed in a supportive way to describe the effect of treatment. Secondary analyses will also be performed on the FAS and with the ANCOVA approach.

Double-blind phase:

The following secondary efficacy analyses will be conducted:

- The analysis of the three co-primary endpoints will be repeated in the three pre-specified subgroups of ED severity: mild, moderate and severe as specified in [Section 14.1](#)
- The change in the IIEF-EF domain, SEP Question 2 and SEP Question 3 at each 4-week visit will be analysed
- Responder analyses assessing the proportion of subjects with a specific increase in the IIEF-EF domain from baseline, using a different responder definition defined separately for each baseline severity group, will be conducted. A responder is defined as having an increase of ≥ 2 , ≥ 5 and ≥ 7 for the mild, moderate and severe subjects, respectively (published Minimal Clinically Important Difference [MCID] according to Rosen *et al.* 2011 [31])
- Responder analyses for SEP Questions 2 and 3 will be conducted in the same way as for the IIEF-EF. A responder is defined as having an increase of -1.3% , 16.7% and 27.3% for SEP Question 2 and 5.0% , 23.3% and 17.0% for SEP Question 3 for patients with mild, moderate and severe baseline ED, respectively (published MCID according to Araujo *et al.* 2012 [32])
- Responder analyses will also be conducted using responder thresholds (that represent meaningful within-patient changes) in the three co-primary endpoints that are determined using a suitable set of data from this study, prior to study unblinding. Receiver operating characteristics (ROC) analyses will be performed to define the thresholds using the PGI-S and PGI-C as anchors, with the thresholds chosen to balance sensitivity and specificity, supplemented with both empirical cumulative distribution functions and probability density functions. The thresholds defined from these analyses will be included in the final SAP prior to breaking the blind.

The following secondary efficacy analyses will be conducted in a more exploratory way making use of the FAS data in the selected doses and placebo over both stages:

- The GAQ will be analysed via logistic regression including terms for treatment group, site and baseline ED severity (categorical variable)
- The change in the other domains of the IIEF questionnaire, the other SEP questions (Questions 1, 4 and 5), the overall SEAR questionnaire score, the scores in the two subdomains of the SEAR questionnaire (sexual relationship satisfaction and confidence) and the PGI-S at time points 4, 8 and 12 weeks will be analysed using ANCOVA as described for the primary endpoint analysis for SEP Questions 2 and 3. The PGI-C will be analysed using an analysis of variance (ANOVA)
- Subjective measures of the time of onset and duration of action (erection) and erection hardness will be analysed using Wilcoxon ranks for each intercourse attempt, averaged across intercourse attempts within each 4-week period for each subject. The averaged Wilcoxon rank data will be analysed using ANCOVA as described for the primary endpoint analysis

- Usage and application question responses will be summarised by treatment group

All efficacy assessments provided by the female partners will be analysed using the same statistical models as for the male subjects.

Open-label extension phase:

Summary statistics for all efficacy measures will be given for actual values and changes from baseline (where applicable), where the baseline assessments are the ones prior to the double-blind phase. Individual components of composite scores (but not domains) will not be summarised unless otherwise stated. Individual components as well as domains will be presented in listings together with the scores used in the analysis.

Summaries of responders at each Visit will be given using the same responder definitions as per the analysis of double-blind phase.

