9.5 Subject Inclusion and Randomisation

Subjects who sign the ICF for the study at Visit 1 and undergo screening procedures will be identified during screening by a unique screening number. Subjects who fulfil the eligibility criteria will be assigned consecutive subject numbers and randomised before study medication is dispensed on Day 1 of the treatment period (Visit 2).

Subjects will be randomised to receive one of the following gel treatments in a 1:1:1:1 ratio according to a parallel group design (i.e. subjects will receive one treatment only):

- MED2005 0.2% (w/w) GTN gel to deliver a 0.6 mg dose of GTN
- MED2005 0.4% (w/w) GTN gel to deliver a 1.2 mg dose of GTN
- MED2005 0.6% (w/w) GTN gel to deliver a 1.8 mg dose of GTN
- Placebo vehicle

Subjects will be stratified for randomisation based on their baseline ED severity scores from the end of the screening period:

- Mild (IIEF-EF domain score of 17–25)
- Moderate (IIEF-EF domain of 11–16)
- Severe (IIEF-EF domain \leq 10)

It is intended to randomise an approximately equal number of subjects for each baseline severity group. No stratification by site will be done as, with four treatment groups and three baseline ED severity strata, it is not deemed feasible without risking overall balance for treatments.

If a subject discontinues from the study, the subject number will not be re-used and the subject will not be allowed to re-enter the study.

Randomisation will be carried out using an IVRS/IWRS.

For the open-label extension phase, eligible subjects who sign the ICF for the extension phase at Visit 6 will continue in the study. All subjects will receive MED2005 0.6% (w/w) GTN gel to deliver a 1.8 mg dose of GTN.

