11.2.5 Patient Global Impression (PGI) Scales

The global assessment tools the PGI-S and PGI-C were included to assess the subjects’ overall perception of their condition. The PGI-S and PGI-C are both 1-item questionnaires using balanced Likert scales that ask the subject to rate the severity of a specific condition (the PGI-S, a single-state 5-point categorical scale) or to rate at a particular timepoint the perceived change in his condition in response to treatment (the PGI-C, a transitional 7-point categorical scale).

The PGI scales were modelled on the Clinical Global Impression scales developed in the 1970s. They are simple, direct and easy to use and can be tailored to specific conditions and disease parameters. The PGI scales have previously been validated for use in a number of conditions including urinary incontinence and chronic pain [28, 29]. The PGI-C has also been validated for the evaluation of patient satisfaction (i.e. EF) after placement of a penile prosthesis [30].

In this study, subjects will be asked to complete the PGI-S at the end of Visit 1 and Visit 2, after completing the IIEF; and the PGI-S and PGI-C at the end of each of the three 4-weekly periods during treatment in the double-blind phase (i.e. Visits 3, 4 and 5 [end of Weeks 4, 8 and 12]). The PGI results will be part of the secondary efficacy endpoint analyses. Further details of the PGI scales are provided in [Section 18.5](#).

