18.5 PGI Scales**PGI-S (Severity) Scale**

Please choose the response below that best describes the severity of your erectile dysfunction over the past 4 weeks.

1. None.
2. Mild.
3. Moderate.
4. Severe.
5. Very severe.

PGI-C (Change) Scale

Please choose the response below that best describes the overall change in your erectile dysfunction since you started using the study treatment.

1. Very much better.
2. Moderately better.
3. A little better.
4. No change.
5. A little worse.
6. Moderately worse.
7. Very much worse.

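### PGI-C is assigned an ANOVA with no terms named, so no continuous baseline is used and adjustment for the stratification factor is not secured; an ANCOVA would be a free improvement

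*Protocol*

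**What the plan says.** Section 14.5.4 opens its secondary analyses with a general rule: "Secondary analyses will also be performed on the FAS and with the ANCOVA approach". Further down, under "The following secondary efficacy analyses will be conducted in a more exploratory way", one bullet sends the other IIEF domains, the remaining SEP questions, SEAR and PGI-S to the ANCOVA used for SEP Questions 2 and 3. Section 14.5.3 defines that model as treatment group, site, continuous baseline and categorical ED severity. The same bullet then says "The PGI-C will be analysed using an analysis of variance (ANOVA"). No terms follow. The synopsis (Section 5, Statistical Methods) repeats the contrast.

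The neighbouring measures without a pre-treatment value are handled as follows.

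- GAQ: "The GAQ will be analysed via logistic regression including terms for treatment group, site and baseline ED severity (categorical variable").
- Onset, duration and hardness questions, asked only on treatment (Section 11.2.6, Table 2): averaged ranks analysed by ANCOVA, with the primary endpoint analysis as the model.

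On design and available data, Section 9.5 says "Subjects will be stratified for randomisation based on their baseline ED severity scores from the end of the screening period", with roughly equal numbers intended in the three groups. Section 11.2.5 says "subjects will be asked to complete the PGI-S at the end of Visit 1 and Visit 2", and Section 14.5.3 says "Baseline for the IIEF-EF score is the assessment at Visit 2". The PGI-C itself (Section 18.5) asks about "overall change in your erectile dysfunction since you started using the study treatment", so it can have no baseline.

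**The concern.** PGI-C cannot be adjusted for its own baseline, and the plan appears to have moved from ANCOVA to ANOVA for that reason. Lacking an own baseline does not require this. Every randomised man is scheduled to have a Visit 2 IIEF-EF, a Visit 2 PGI-S and a severity stratum, and the plan does adjust other measures that have no baseline. Section 14.5.3 gives one reason for leaving severity out of a model: for IIEF-EF it is already present as a continuous variable. That reason does not apply to PGI-C.

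What is at stake is efficiency and consistency. If baseline status predicts the PGI-C rating, the intervals are wider than the collected data allow. If the stratifying factor is omitted and is prognostic, the reported standard error is too large for the design. PGI-C would also be read beside GAQ, SEP, SEAR and PGI-S results that are adjusted for severity.

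**Working it through.** **Figures in the plan.** The protocol states no effect, SD or power for PGI-C, so there is no PGI-C figure to reproduce. Its one power figure (Section 14.7) is 90% for all three co-primary endpoints at 250 per group. With differences 3.2, 11.5 and 12, SDs 5.6, 33 and 33, correlations 0.5, 0.5 and 0.6, and two-sided alpha 0.05/3, the marginal powers are 99.997%, 93.3% and 95.3%. The joint power is 90.4%. The stated figure holds, and it does not depend on the PGI-C model.

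**What the ANOVA sentence can mean.**

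| Reading | Severity | Continuous baseline |
|---|---|---|
| SEP model without its baseline term: treatment, site, severity | in | not used |
| Treatment and site, or treatment alone | out | not used |

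The text does not choose between the rows. The last column is the same in both.

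**Size of the gain.** Let R² be the share of PGI-C variance explained by the baseline terms that are added. R² is an assumption throughout. The interval width is multiplied by √(1 − R²), and the equivalent increase in sample size is 1/(1 − R²) − 1.

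| Assumed R² | √(1 − R²) | Interval narrower by | 1/(1 − R²) | Equivalent to |
|---|---|---|---|---|
| 0 | 1.000 | 0% | 1.000 | no gain |
| 0.05 | 0.975 | 2.5% | 1.053 | 5% more men |
| 0.10 | 0.949 | 5.1% | 1.111 | 11% more men |
| 0.15 | 0.922 | 7.8% | 1.176 | 18% more men |

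**Power, for illustration.** Assume a standardised effect of 0.25, with n = 250 per group and two-sided alpha 0.05/3 = 0.0167 (critical value 2.394). Nominal power is Φ(0.25/√((1 − R²)·2/250) − 2.394):

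- R² = 0: 65.6%
- R² = 0.05: 68.2%
- R² = 0.10: 71.0%

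**If severity is the prognostic term and is left out.** Balanced stratified randomisation already removes between-stratum variation from the treatment contrast, but the unadjusted standard error does not reflect this. The true test size is 2·(1 − Φ(2.394/√(1 − R²))). That is 0.0140 at R² = 0.05 and 0.0116 at R² = 0.10, against a nominal 0.0167. Actual power in the same illustration is Φ((0.25/√(2/250) − 2.394)/√(1 − R²)), which gives 66.0% and 66.4%, against 68.2% and 71.0% with adjustment. The contrast stays unbiased in both cases.

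**The case against.** The strongest reply is that the sentence lists no terms at all, not even treatment. Severity and site are categorical, and an ANOVA can hold both. A natural reading is the SEP model without its continuous baseline, which gives the same factors as the GAQ model. Section 14 leaves further detail to the SAP, and naming the factors of an exploratory model is ordinary SAP content. This stands as far as it goes. A reader might infer that the protocol prescribes a one-way ANOVA, or that it excludes baseline ED severity. The text says neither, and that inference rests only on silence. The reply does not rescue the continuous baseline, however: the contrast with ANCOVA within one bullet is a stated choice of method, and it sits awkwardly with the general rule for secondary analyses.

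A second reply is that the gain is conditional. No document links PGI-C to baseline severity, and R² could be zero. That is right, and the range above therefore starts at zero.

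A third reply is that adding Visit 2 IIEF-EF gives PGI-C a covariate set that none of the other secondary scales has. That is also true, but it parallels the SEP model, with a collected baseline standing in for the one PGI-C lacks. Section 14.5.3 already uses the same four terms in its sensitivity analysis of IIEF-EF.

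**Conclusion.** The point holds as a free improvement. The stated method uses no continuous baseline and does not secure adjustment for the stratification factor, while comparable measures in the same section are adjusted. Under an assumed R² of 0 to 15%, the intervals would be about 0 to 8% narrower with adjustment, which is worth 0 to 18% more men. If severity is omitted and prognostic, the test is conservative.

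Two stronger conclusions are tempting and are not supported. The PGI-C result would not be biased: randomisation protects the contrast under any of these models. Nor does the choice weaken the trial's efficacy claim: PGI-C is exploratory, and efficacy is declared on the three co-primary endpoints, whose analysis and sample size are untouched. It would also be wrong to treat the GAQ as the only other measure without a baseline, because the onset, duration and hardness questions have none either.

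**What to change.** In Section 14.5.4, replace the PGI-C sentence with: *PGI-C at Weeks 4, 8 and 12 will be analysed by ANCOVA with treatment group, site, baseline ED severity (categorical) and Visit 2 IIEF-EF (continuous).* Make the same change in the synopsis. If the sponsor prefers to keep an ANOVA, the minimum is to name its factors as treatment group, site and baseline ED severity, matching the GAQ model; that secures the stratification factor but leaves the continuous baseline unused.

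The cost is one sentence in two places. No new data, visits or subjects are needed. The added terms use three degrees of freedom (two for severity, one for IIEF-EF) out of 1000 planned men, so little is lost if baseline turns out not to be prognostic.
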